## 5.2 Analysis Sets

The following populations are defined:

Population	Description	
Randomized	All participants with data in the CRF.	
Full analysis set (FAS)	Subset of randomized participants who received at least 1 dose of the study vaccine or control vaccine and had a valid post-vaccination blood sample result.	
	Participants will be analyzed according to the intervention to which they were randomized.	
Safety Analysis Set (SafAS)	Participants who have received at least 1 dose of the study vaccines. All participants will have their safety analyzed according to the vaccine they actually received.	
	Safety data recorded for a vaccine received out of the protocol design will be excluded from the analysis (and listed separately).	
Per-protocol analysis set (PPAS)	Subset of the FAS. Participants presenting with at least one of the following relevant protocol deviations will be excluded from the PPAS:	
	Participant is not YF-naïve	
	Participant is recruited in Asia	
	• Participant did not meet all protocol-specified inclusion criteria or met at least one of the protocol-specified exclusion criteria	
	• Participant received a vaccine other than the one that he / she was randomized to receive	
	• Preparation and / or administration of vaccine was not done as per- protocol	
	Non-availability of other critical measurements for the primary analysis:	
	• Baseline serology sample was not collected in the protocol-specified time window or the serology sample was not drawn	
	• Participant did not provide the post-dose serology sample on Day 29 Visit (D28 after vaccination) in the proper time window or the blood sample was not drawn	
	• Participant received any therapy / medication / vaccine which could inhibit the immune response until the time point considered for the analysis (Day 29, Visit 4).	
	• In addition to the reasons listed above, participants will also be excluded from the PPAS if their baseline or post-vaccination serology sample at D29 (Visit 4) did not produce a valid test result (ie, results for all antigens are missing or out-of-range).	

	· · · · · · · · · · · · · · · · · · ·
	This list may not be exhaustive. The above protocol deviations leading to exclusion from the PPAS may be detailed and completed if necessary, in the SAP following a data review. The PPAS definition will be finalized before the database lock (and code-breaking if applicable). In the event of a local or national immunization program with a eg, pandemic influenza vaccine, any other vaccine as needed, participants who receive 1 or more doses of eg, a pandemic influenza vaccine, or the vaccine listed above at any time during the study will not be withdrawn from the study.
Subgroup-Per-Protocol Analysis Set (sub-PPAS)	Subset of the PPAS. Participant will be excluded from the sub-PPAS if they did not provide the post-dose serology on Day 29 Visit (D28 after vaccination) in the proper time window of original protocol (D29 +3 days).

The PPAS will be used for the analysis for the primary objectives. Immunogenicity analyses in secondary objectives will be performed on FAS and a complementary analysis will be provided on sub-PPAS. Demographic and baseline characteristics will be presented on the PPAS and FAS.

The SafAS will be used for the description of clinical safety.

Randomized participants will be used for various standard population tables including duration of the study, disposition of participants and deviations and exploratory objective.

The subset will be used to describe additional neutralizing Ab levels in this subset.

## 5.3 Handling of Missing Data and Outliers

## 5.3.1 Immunogenicity

No imputation of missing values and no search for outliers will be performed. LLOQ and ULOQ management will be performed as described above.

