#### Rationale:

A first study, VYF01, aimed to assess the safety, viremia and immune responses of 3 dosages of vYF and YF-VAX, as a control vaccine, is ongoing in the USA. A second planned study, VYF02, aims to assess the non-inferiority of the immune response of the investigational vaccine candidate vYF to the licensed YF-VAX vaccine in adults in the USA.

The proposed third study VYF03 is a Phase II, randomized, observer-blind, active-controlled (Stamaril) multi-center study to assess the non-inferiority of the immune response, in terms of seroconversion rates of the investigational vaccine candidate vYF to the licensed Stamaril, in adults aged 18 years up to 60 years in Europe (EU). The safety and immunogenicity profile of vYF in a cohort of Asian population of Chinese origin outside of China will also be presented. The study will also assess the immunogenicity profiles (seroprotection rates, geometric mean of titers [GMT] and geometric means of the individual titer ratios [GMTR]) and the safety profiles of vYF and Stamaril.

Stamaril, the Sanofi Pasteur YF vaccine currently licensed and in use in more than 100 countries (including European and some Asian countries) will be the control vaccine.

For the non-inferiority VYF03 study in EU, it is planned to enroll 570 participants into 2 groups in a 2:1 ratio: 380 participants will be administered vYF and 190 participants will be administered Stamaril on D01. In VYF03 in Asia, it is planned to enroll 120 participants also distributed into 2 groups in a 2:1 ratio: 80 participants will be administered vYF and 40 participants will be administered Stamaril on D01. The participants in Asia (80 and 40 in the vYF and Stamaril groups, respectively) will be enrolled for descriptive purposes only.

In addition, the study aims to assess the immune responses induced by the YF vaccines in terms of seroprotection and seroconversion rates, GMT, GMTR, depending on FV serostatus at baseline (eg, YF, Dengue and Zika viruses, as well as Japanese encephalitis [JE] virus in Asia), as well as the safety profiles. The persistence of the immune response over time, up to 5 years post-vaccination, will be assessed yearly.

VYF03 assessment will be based on immunogenicity and safety profiles of the vYF vaccine in comparison to Stamaril.

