### International Certificate of Vaccination or Prophylaxis for YF Vaccination

At the end of the first interim analysis and at the end of the study, the Investigators will be provided with individual listings detailing for each participant the vaccine group assignment and the neutralizing antibody titers at the successive time points. Participants are responsible for

contacting the study site to obtain this information about which study group they were assigned to and which vaccine they received.

VYF03

Those participants enrolled in the Stamaril group can be provided by the investigational site with the ICVP for YF vaccination; and those participants enrolled in a vYF group would be informed that they need to obtain a licensed YF vaccine prior to travel to endemic areas.

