#### 4.4 **End of Study Definition**

A participant is considered to have completed the study if he/she has completed the last visit planned in the SoA.

The end of the study is defined as the date of the last visit of the last participant in the study.

However, for periodic safety reports, the study is considered completed when the clinical study report is finalized.

All participants enrolled in this study will be followed up for 5 years after vaccine administration. They will be kept in the study (and so, will not be withdrawn) even if they fail to come to one or more of the yearly visits during the 5-year follow-up.

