## 5.1.2.2 Statistical Methods

#### Immunogenicity:

Analyses will be performed on the Full Analyses Set.

The immunogenicity parameters will be described per vaccine group. Immunogenicity analyses will be provided on participants by YF serostatus and by FV serostatus.

The following parameters will be analyzed:

- GMT for each vaccine group
- Seroconversion rates: number and percentage of participants in each vaccine group converted with neutralizing antibody titer 4-fold increased compared to D01 up to M6: D11 (subset only) compared to D01, D29 compared to D01, M6 compared to D01; and yearly from Y1 to Y5 compared with the latest planned timepoint: Y1 compared to M6, Y2 compared to Y1, Y3 compared to Y2, Y4 compared to Y3, Y5 compared to Y4
- Within-group GMTR for each vaccine group post-vaccination injection, compared to D01 (D11/D01 [subset only], D29/D01, M6/D01 and yearly ratios: Y1/M6, Y2/Y1, Y3/Y2, Y4/Y3, Y5/Y4

- Number and percentage of participants (seroprotection rates) in each vaccine group with antibody titer ≥ 10 (1/dil) at baseline (D01) and at D11 (subset only†), D29, M6, and yearly from Y1 to Y5
- Distribution of titers against YF at each time point and corresponding RCDC

The 95% CIs will be calculated using:

- The normal approximate method for GMTs and GMTRs
- The exact binomial distribution for percentages (Clopper-Pearson's method, quoted by Newcombe)

Assuming that log10 transformation of the titers/ratios follows a normal distribution, first, the mean and 95% CI will be calculated on log10 (titers/ratios) using the usual calculation for normal distribution, then antilog transformations will be applied to the results of calculations, to compute GMTs/GMTRs and their 95% CIs.

Complementary immunogenicity analysis based on the planned analysis on D29 with a time window of +3 days will be performed on a sub-population of the Per-Protocol Analysis Set:

- Non-inferiority analysis of the antibody response on D29
- GMT for each vaccine group
- Seroconversion rates: number and percentage of participants in each vaccine group converted with neutralizing antibody titer 4-fold increase compared to the previous time point, at D29 compared to D01
- Within-group GMTR for each vaccine group D29 post-vaccination injection, compared to D01
- Number and percentage of participants (seroprotection rates) in each vaccine group with antibody titer  $\geq 10$  (1/dil) at baseline (D01) and at D29

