517 -vYF			

\* Subset only

M: Number of participant s available for the endpoint

YF status: Immune for participants with quantified ( $\geq$  LLOQ) neutralizing Abs against YF; naive for participants without quantified (< LLOQ) neutralizing Abs against YF in the baseline sample

SAP Core Body for VYF03

FV status			vYF (N=###)				Stamaril (N=###)		
	Time point/ratio	М	GM	(95% CI)	Μ	GM	(95% CI)		
Immune	V01 (Pre-inj)	###	###.#	(###.#; ###.#)	###	###.#	(###.#; ###.#		
	V02 (V01+10D)*	###	###.#	(###.#; ###.#)	###	###.#	(###.#; ###.#		
	V04 (V01+28D)	###	###.#	(###.#; ###.#)	###	###.#	(###.#; ###.#		
	V05 (V01+6M)	###	###.#	(###.#; ###.#)	###	###.#	(###.#; ###.#		
	V06 (V01+1Y)	###	###.#	(###.#; ###.#)	###	###.#	(###.#; ###.#		
	V07 (V01+2Y)	###	###.#	(###.#; ###.#)	###	###.#	(###.#; ###.#		
	V08 (V01+3Y)	###	###.#	(###.#; ###.#)	###	###.#	(###.#; ###.;		
	V09 (V01+4Y)	###	###.#	(###.#; ###.#)	###	###.#	(###.#; ###.;		
	V10 (V01+5Y)	###	###.#	(###.#; ###.#)	###	###.#	(###.#; ###.		
	Ratio V02 (V01+10D)/ V01 (Pre-inj)	###	###.#	(###.#; ###.#)	###	###.#	(###.#; ###.		
	Ratio V04 (V01+28D)/ V01 (Pre-inj)	###	###.#	(###.#; ###.#)	###	###.#	(###.#; ###.		
	Ratio V05 (V01+6M)/ V01 (Pre-inj)	###	###.#	(###.#; ###.#)	###	###.#	(###.#; ###.		
	Ratio V06 (V01+1Y)/ V05 (V01+6M)	###	###.#	(###.#; ###.#)	###	###.#	(###.#; ###.		
	Ratio V07 (V01+2Y)/ V06 (V01+1Y)	###	###.#	(###.#; ###.#)	###	###.#	(###.#; ###.		
	Ratio V08 (V01+3Y)/ V07 (V01+2Y)	###	###.#	(###.#; ###.#)	###	###.#	(###.#; ###.		
	Ratio V09 (V01+4Y)/ V08 (V01+3Y)	###	###.#	(###.#; ###.#)	###	###.#	(###.#; ###.		
	Ratio V10 (V01+5Y)/ V09 (V01+4Y)	###	###.#	(###.#; ###.#)	###	###.#	(###.#; ###.;		
Naïve									

Table 7.3: Summary of geometric means of titers and geometric means of individual titer ratios of antibody against YF virus by FV status atbaseline - Microneutralization assays - Full Analysis Set

Confidential/Proprietary Information Page 41 of 51

Sanofi Pasteur	SAP Core Body for VYF03
517 -vYF	

\* Subset only

M: Number of participant s available for the endpoint

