	V05 (V01+6M)/ V01 (Pre-inj)	###/###	##.#	(##.#; ##.#)	###/###	##.#	(##.#; ##.#)		
	V06 (V01+1Y)/ V05 (V01+6M)	###/###	##.#	(##.#; ##.#)	###/###	##.#	(##.#; ##.#)		
	V07 (V01+2Y)/ V06 (V01+1Y)	###/###	##.#	(##.#; ##.#)	###/###	##.#	(##.#; ##.#)		
	V08 (V01+3Y)/ V07 (V01+2Y)	###/###	##.#	(##.#; ##.#)	###/###	##.#	(##.#; ##.#)		
	V09 (V01+4Y)/ V08 (V01+3Y)	###/###	##.#	(##.#; ##.#)	###/###	##.#	(##.#; ##.#)		
	V10 (V01+5Y)/ V09 (V01+4Y)	###/###	##.#	(##.#; ##.#)	###/###	##.#	(##.#; ##.#)		
Naive	•••			. , , ,			· · · · ·		

n: Number of participant s who achieve a yellow fever vaccination seroconversion.

M: Number of participant s with available data for the endpoint.

Seroconversion: For a participant with a 4-fold increase in NAb titers as compared to the previous timepoint value

Flavivirus status: Immune for participants with quantified ( $\geq$  LLOQ) neutralizing Abs against YF, and/or against at least one dengue serotype, and/or Zika  $\geq$  100 (1/dil) in the baseline sample, and/or JE in Asia; naive for participants without quantified ( $\leq$  LLOQ) neutralizing Abs against YF, with no Ab quantified against any of the four dengue serotypes and Zika  $\leq$  100 (1/dil) and JE in Asia; in the baseline sample.

YF status	Time point		vYFv (N=xxx)		Stamaril (N=xxx)			
		n/M	Seroprotection rate (%)	95% CI	n/M	Seroprotection rate (%)	95% CI	
Immune	V01 (Pre-inj)	###/###	##.#	(##.#; ##.#)	###/###	##.#	(##.#; ##.#)	
	V02 (V01+10D)*	###/###	##.#	(##.#; ##.#)	###/###	##.#	(##.#; ##.#)	
	V04 (V01+28D)	###/###	##.#	(##.#; ##.#)	###/###	##.#	(##.#; ##.#)	
	V05 (V01+6M)	###/###	##.#	(##.#; ##.#)	###/###	##.#	(##.#; ##.#)	
	V06 (V01+1Y)	###/###	##.#	(##.#; ##.#)	###/###	##.#	(##.#; ##.#)	
	V07 (V01+2Y)	###/###	##.#	(##.#; ##.#)	###/###	##.#	(##.#; ##.#)	
	V08 (V01+3Y)	###/###	##.#	(##.#; ##.#)	###/###	##.#	(##.#; ##.#)	
	V09 (V01+4Y)	###/###	##.#	(##.#; ##.#)	###/###	##.#	(##.#; ##.#)	
	V10 (V01+5Y)	###/###	##.#	(##.#; ##.#)	###/###	##.#	(##.#; ##.#)	
Naive	•••							

Table 7.6: Summary of percentages of participants achieving seroprotection after one dose YF vaccination by YF status at baseline -Microneutralization assays - Full Analysis Set

\*Subset only.

n: Number of participant s who achieve a yellow fever vaccination seroprotection.

M: Number of participant s with available data for the endpoint.

Seroprotection: Participants with antibody titer  $\geq 10$  (1/dil)

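### Year 1 to Year 5 titres are summarised only on those who attend each visit, so the 5-year persistence estimates are unbiased only if attendance is unrelated to titre

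*SAP*

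**What the plan says.** Long-term immunity is a stated aim. The Protocol synopsis (Rationale) says: "The persistence of the immune response over time, up to 5 years post-vaccination, will be assessed yearly". Protocol 4.4 and 7.2 keep participants in the study "even if they fail to come to one or more of the yearly visits during the 5-year follow-up", so gaps are foreseen.

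The analysis has four parts:

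- **Set.** SAP 5.1.2.2 uses the FAS. Under SAP 5.2 this needs one dose and that the participant "had a valid post-vaccination blood sample result". Attendance at later visits is not required.
- **Estimates.** GMTs and GMTRs are means of log10 values with a normal-theory interval, visit by visit. Rates are simple proportions. Seroconversion and ratios after M6 are paired: "Y1 compared to M6, Y2 compared to Y1, Y3 compared to Y2, Y4 compared to Y3, Y5 compared to Y4".
- **Denominators.** The GMT and GMTR shells (SAP Tables 7.2 and 7.3) define "M: Number of participant s available for the endpoint". The seroconversion and seroprotection shells (Tables 7.4 to 7.7) define "M: Number of participant s with available data for the endpoint".
- **Missing data.** SAP 5.3.1: "No imputation of missing values and no search for outliers will be performed".

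Neither document contains a longitudinal model, weighting, a completer analysis or a missing-data sensitivity analysis for these visits.

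Protocol 2.3.2 provides for listings to investigators at the end of the first interim analysis and at the end of the study. They show each participant's vaccine group "and the neutralizing antibody titers at the successive time points". Participants may ask the site which vaccine they received. Stamaril recipients can be given the vaccination certificate, while vYF recipients are told they need a licensed vaccine before travel to endemic areas.

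**The concern.** A row of yearly GMTs will be read as waning in one population. As planned, each row can describe a different set of people. An absent participant's D29, M6 and earlier yearly titres count at the visits attended, and in complete adjacent pairs, but they do not inform the later estimates even though they predict the missing values.

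This matters if attendance depends on titre. The plan contains a possible route: investigators hold assignment and titres after the first interim analysis, participants can learn their vaccine, and travel advice then differs by arm while yearly follow-up continues. What is at stake is the description of 5-year persistence per vaccine group.

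**Working it through.** **The plan's own figure.** The only retention figure is for D29 in the EU (SAP 5.5): 456/570 = 304/380 = 152/190 = 0.80. It covers evaluability for the primary analysis and says nothing about Y1 to Y5. All long-term values below are therefore assumptions.

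**Pairs lost to intermittent misses.** If each visit is missed independently with probability m, a yearly ratio is available for (1 − m)² of participants:

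- m = 5%: 0.95² = 0.90
- m = 10%: 0.90² = 0.81
- m = 20%: 0.80² = 0.64

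One missed visit can cost two ratios.

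**Bias in the Y5 GMT.** Simulation assumptions:

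- 380 participants (the planned EU vYF arm)
- seven visits (D29, M6, Y1 to Y5)
- log10 SD 0.45 and exchangeable correlation 0.70 or 0.85
- drop-out from Y1, with odds depending on the previous titre

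| Odds of leaving per SD lower titre | Planned Y5 GMT, 20% lost | Planned Y5 GMT, 35% lost | Repeated-measures model |
|---|---|---|---|
| 1.0 | within 1% | within 1% | within 1% |
| 1.3 | +4.0% to +5.5% | +8.6% to +9.7% | within 0.4% |
| 1.6 | +7.7% to +10.0% | +15.2% to +18.3% | within 0.4% |

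A rerun gave about 5% to 10% and 8% to 19%. Letting loss depend only on the M6 titre gave about 4% to 9% and 7% to 15%. Together, the range is about 4% to 10% at 20% loss and 7% to 19% at 35% loss.

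The shifts behind these figures are small: log10(1.10)/0.45 = 0.09 SD and log10(1.19)/0.45 = 0.17 SD. The simulated distribution is symmetric, so if high responders leave with the same odds the factors invert. At 20% loss the Y5 GMT is then 1/1.04 = 0.96 to 1/1.10 = 0.91 of its true value, and at 35% loss 1/1.07 = 0.93 to 1/1.19 = 0.84.

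**Precision when there is no bias.** At 35% loss unrelated to titre, the standard error of the Y5 mean log10 titre is 0.029 to 0.030 as planned and 0.026 to 0.027 from the model, about 7% to 13% smaller.

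**Wider assumptions.** A second simulation used 460 participants, SD 0.4 to 0.6, correlation 0.6 to 0.8 and base drop-out of 3% to 10% a year. The planned Y5 GMT was 1.05 to 1.30 times truth at odds of 1.65 per SD lower previous titre, and 1.12 to 1.65 times truth at odds of 2.7. The model gave 0.99 to 1.01.

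The two planned displays erred in opposite directions. Over both odds, a true Y5/M6 fold of 0.251 appeared as 0.263 to 0.416 from per-visit GMTs (waning understated). It appeared as 0.188 to 0.246 if the paired yearly ratios are multiplied together (waning overstated). The SAP does not plan that multiplication, but a reader could do it.

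**The case against.** Most of the case for leaving the plan alone has substance.

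- **The effect is conditional.** With loss unrelated to titre there is no bias, and neither document shows that attendance depends on titre. A reader might infer that the persistence curve is already known to mix waning with drop-out, or that selective attendance must raise it. The documents support neither, and the sign reverses if high responders leave.
- **Earlier titres are not discarded.** They count at every visit attended. They are only not used to inform later visits.
- **The route is narrower than it may appear.** A reader might infer that participants learn their titres. Protocol 2.3.2 gives titres to investigators and lets participants learn their group and vaccine; onward release of titres is an inference. Under SAP 5.4 and 5.7 the first interim analysis covers data to M6, so no Y1 to Y4 titre is released this way before study end.
- **The endpoint is descriptive.** Protocol 9.1 and 9.4.2 and SAP 5.1.2.1 plan no Y1 to Y5 test, margin or decision rule. With SD 0.45 the 95% interval for one arm's Y5 GMT has a half-width of 1.96 × 0.45/√304 = 0.0506 log10 (12%) at 20% loss of 380, and 1.96 × 0.45/√247 = 0.0561 (14%) at 35% loss. The bias at 20% loss lies inside that.
- **There is some protection.** M is printed for each visit, ratio and arm. Protocol 7.3 requires missed visits to be chased. Paired ratios compare the same people at adjacent visits, but they do not cure titre-related loss.
- **The model's near-perfect result is almost built in.** Loss driven by an observed titre in correlated normal data is what such a model assumes, and no censoring at the LLOQ was reported in the simulations. Substituting 5 below the LLOQ in a normal model is untested here.

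These points limit the severity and shape the fix. They do not remove the gap, because the planned means need a stricter assumption than missing at random, and nothing pre-specified tests it.

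**Conclusion.** The point holds in conditional form. Y1 to Y5 GMTs, yearly ratios and rates are available-case summaries in a study that expects missed yearly visits. They are unbiased if attendance is unrelated to titre, and biased in the direction set by who leaves if it is not.

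Under the assumed values, with low responders leaving, the Y5 GMT would be about 4% to 10% too high at 20% loss and 7% to 19% too high at 35% loss. SD, correlation, loss and the strength of selection are all assumptions.

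Seroprotection moves less predictably. In the worst of these cases (odds 1.6, 35% loss) the shift is at most about 0.7 points if the true Y5 GMT is 100 or 300, and about 2 to 4 points if it is 30 to 50. A reader might also infer a different bias in each arm. That is possible once assignment is known, but it has not been quantified.

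This is an inexpensive improvement to a secondary, descriptive analysis. The D29 primary comparison is unaffected.

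**What to change.** Add to SAP 5.1.2.2, as a supportive analysis:

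1. A likelihood-based repeated-measures model of log10 YF titre from D29 to Y5 in YF-naïve FAS participants, with arm, visit, arm by visit and unstructured covariance.
2. Values below the LLOQ treated as left-censored, or sensitivity shown to the substituted value of 5.
3. Titres taken after a recorded commercial YF vaccination excluded from the persistence estimate. Protocol 6.5 collects these vaccinations for the whole study, but the FAS has no rule for later titres.
4. Back-transformed model GMTs with 95% CI beside the planned observed GMTs, with M and reasons for absence by arm and visit.
5. One missing-not-at-random sensitivity analysis.

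Model-based imputation of seroprotection is optional.

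The cost is SAP wording and some programming, with no new data or visits. The downside is a missing-at-random and log-normal assumption, which stays visible because the observed values remain in the table.

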## 5.3.2 Safety

Generally, no replacement will be done for Safety Missing Data and Outliers.

## 5.3.2.1 Immediate

For unsolicited systemic AEs, a missing response to the "Immediate" field is assumed to have occurred after the 30-minute surveillance period and will not be imputed.

